3.1 Overall study design

This is an open-label, one-group, multicentre, phase II study conducted to investigate PFS in patients treated with imatinib longer than 5 years for oligo-metastatic GIST (\leq 3 metastases) and who have no detectable overt GIST lesions in CT/MRI imaging following complete surgical resection (R0/R1-resection), RFA of the metastases, or after systemic treatment for oligometastatic GIST.

The study participants are assigned to stop imatinib and will be monitored for cancer progression longitudinally with physical examination, measuring blood cell counts and blood chemistry, and with CT/MRI examinations. A pre-planned interim analysis will be carried out when the first 15 patients in the study have been follow-up of for one year. The study will be terminated if 10 or more of the 15 patients (\geq 67 %) have recurrence of GIST or discontinue the study within the first 12 months from the date of study entry. The primary analysis of the study will be carried out when the median follow-up time of the study patients is at least 36 months. A total of 31 patients will be enrolled. If GIST recurs, imatinib will be restarted at the same dose as at study entry.

3.2 Study population

3.2.1 Patient population

Patients with advanced (metastatic) GIST with

1) Imatinib treatment longer than 5 years for advanced GIST.

2) \leq 3 metastases detected during the course of the disease and who have no detectable overt GIST lesions in CT/MRI imaging following complete surgical resection (R0/R1-resection) of the metastases, RFA of the metastases, or whose metastases are no longer detectable by imaging (CR).

3.2.2 Inclusion and exclusion criteria

Inclusion criteria:

To be eligible for inclusion in the study, each patient must fulfil each of the criteria below.

1. Age \geq 18.

2. Morphological and immunohistochemical documentation of GIST (immunostaining for KIT/(CD117) and/or DOG-1 (anoctamin-1)) must be positive on a tumour sample. Patients with demonstrated mutation in *KIT* or *PDGFRA* may be entered to the study despite negative immunostaining for KIT and DOG-1 provided that tumour histology is compatible with GIST.

3. > 5.0 years of treatment with imatinib for metastatic disease when the breaks in imatinib administration are taken into account.

4. No more than 3 detectable metastases in the liver and/or in the abdomen in imaging of the abdomen and the pelvis during the course of the disease or at surgery.

5. Confirmed metastatic GIST in history by radiology, histology, or both.

6. Macroscopically complete resection of all metastases (either R0 or R1 surgery). Patients who have microscopically infiltrated margins (or suspected microscopical infiltration, R1) are

allowed to enter the study. RFA of liver metastasis is allowed in place of surgery. Patients whose oligometastatic disease had disappeared completely so that no remaining target lesion for surgery or RFA can be identified (including absence of residual cyst-like lesions) are allowed to enter the study.

7. Eastern Co-operative Oncology Group (ECOG) performance status ≤ 2 .

8. Patient has provided a written, voluntary informed consent prior to study entry and any study-specific procedures.

Exclusion criteria:

To be eligible for inclusion in the study, each patient must not have any of the criteria below.

1. Patients with metastases outside of the abdomen (e.g. in the bones or lungs).

2. Not willing to donate tumor tissue and/or blood samples for the molecular studies that aim at predicting of GIST recurrence.

- 3. Presence of an *SDH* mutation or other evidence for SDH deficiency.
- 4. Presence of neurofibromatosis-1.
- 5. R2 resection of the primary tumor or metastasis.
- 6. Patient with inability to grant reliable informed consent.
- 7. Inability to comply with the scheduled follow-up.

8. Progressive disease during imatinib or other systemic treatments for GIST, or before or after surgery/RFA of the metastases.

3.3 Study assignment

Informed consent must be obtained before any testing of a patient's eligibility is carried out.

Patients who meet the inclusion criteria and none of the exclusion criteria for the study will be registered and given a specific study identity number at the Oslo University Hospital (OUS) secretariat.

The centre must keep a log of all patients who received patient information and/or the consent form of the study, including also those patients who were eligible to the study but who did not wish to participate in the study. The log contains the patient initials, the date when the patient information/consent form was received by the patient, patient eligibility to the study, the decision on study participation, and the decision to consent for collection of survival outcome data.

3.4 Patients and treatments

3.4.1 Study patients

The patients assigned to the study arm discontinue imatinib within 14 days of the date of study inclusion (the date of registration to the study).

Imatinib will remain discontinued until one of the following will occur:

- GIST recurrence
- Withdrawal from the study

3.4.2 Patient discontinuation in the study

The reasons for patient discontinuation in the study must be captured on the CRFs. If the patient discontinues the study, the reason is categorized in the CRFs as one of the following:

- 1. Withdrawal from the study
- 2. GIST progression
- 3. Death (from GIST or from an inter-current cause)
- 4. Other (for example, severe protocol violation, administrative problems)

Relevant information that is related to the reason for study discontinuation, including possible contributory factors, will be included on the CRF.

3.4.3 Concomitant therapy

Administration of any other anticancer agents including other TKIs, chemotherapy, biological agents, or experimental agents is NOT permitted. The patients should receive the medication indicated for their concomitant diseases.

3.4.4 Treatment after disease progression

Treatment after disease progression is usually imatinib, which may be restarted at the same dose as was given before study entry. Imatinib after GIST progression will be administered and monitored according to the institute standard procedures.

3.4.5 End of study

The end of study is defined as the last subject's last visit, defined as either the date of the last visit of the last subject to complete the study or the date at which the last data point from the last subject (required for statistician analysis) was received, whichever is the later date.

3.5 Visit schedule and assessments

3.5.1 Visit schedule

Patient must be followed at the study centre according to the table 1 "Visit schedule and assessments".

The subjects will be followed with CT/MRI at 3-month intervals during the first year in the study arm, 4-month intervals the second and third year, and at 6-month intervals year four and five. The minimum duration of follow-up is 5 years as calculated from the date of study entry, but follow-up for 10 years after study entry is recommended using annual imagining of the abdomen. When clinically indicated, more frequent follow-up visits and CT/MRI imaging

may be organized. All routine assessments must be performed within \pm 28 days of the day indicated on the visit schedule.

3.5.2 Screening assessments

Written informed consent must be obtained before any study specific medical procedures are performed. The screening assessments are done when the patient is on imatinib.

Immunohistochemical evidence of KIT or DOG-1 overexpression must exist at the study entry, and tumour *KIT* and *PDGFRA* mutation analysis needs to be available. However, patients with demonstrated mutation in *KIT* or *PDGFRA* may be entered to the study despite negative immunostaining for KIT and DOG-1 provided that tumour histology is compatible with GIST. An attempt to sequence all frequently mutated *KIT* and *PDGFRA* exons may be made during the study from the stored tumour material.

The demographic data collected includes age, gender and race. As far as possible other data will be collected and includes the date of first GIST histological diagnosis, type of surgical resection (R0 or R1) and GIST characteristics (tumour longest diameter in centimetres, location in the GI tract/abdomen, tumour rupture before or at surgery, and mitotic count per 50 HPFs and/or 5 mm² of the microscope), and whether adjuvant imatinib was given, for how long, and at which dose. Also, if possible, location of metastases (liver or peritoneal cavity), type of resection of metastases (R0 or R1), whether RFA is done, size of metastases (the longest diameter in centimetres), and response to imatinib treatment (complete/partial pathological response) should be collected. The dates of metastasis surgery and/or RFA will also be captured on the CRFs (if done). The imatinib dose administered is recorded, as well as the starting date of imatinib, the highest and the lowest dose of imatinib used for a time period longer than 2 weeks, interruptions of imatinib dosing lasting longer than 2 weeks, and major prior imatinib side-effects (grade 1-4), if any.

Physical examination and assessment of the ECOG performance status are carried out, and height and weight are recorded. In the event that haematology or biochemistry evaluation have been performed within 14 days from the date of inclusion, this evaluation needs not to be repeated, and may be used as the Day 1 values.

CT or MRI of the abdomen and the pelvis must be performed within 28 days prior to the study entry. If CT or MRI has been performed within 28 days from the date of inclusion, it does not need to be repeated.

3.5.3 Tumour assessments

Tumour assessments should be performed with the same method (CT or MRI) throughout the study. All assessments should be performed within 28 days of the scheduled day of assessment, and whenever clinically indicated otherwise.

Radiological tumour assessment at inclusion and if progression should be stored at the local study site and submitted for central review per request.

3.5.4 Laboratory assessments and physical examination

3.5.4.1 Laboratory evaluations

Laboratory analyses will be carried out according to the Visit Schedule. Laboratory values will be recorded on the Follow-up Form (circle the correct range) even when normal.

Haematology

Haematology includes assessment of haemoglobin, total WBC count, platelet count, and a differential count including neutrophils, lymphocytes, monocytes, eosinophils and basophils.

Biochemistry

Biochemistry includes serum or plasma creatinine; serum albumin, total protein, total bilirubin, alkaline phosphatase, AST (SGOT), ALT (SGPT). Lactate dehydrogenase (LDH), and magnesium, calcium and phosphate (Pi) will be performed at 2 months and 5 months on study.

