	 deficiency. 4. Presence of neurofibromatosis-1. 5. R2 resection of the primary tumour or metastasis. 6. Patient with inability to grant reliable informed consent. 7. Inability to comply with the scheduled follow-up. 8. Progressive disease during imatinib or other systemic treatments for GIST before or after surgery/REA of the
STUDY TOEATMENT	metastases. Study group: Discontinuation of imatinib
STUDI IREATMENT	No imatinib or other anti-cancer treatment will be administered.
ASSESSMENTS:	 Primary: Progression-free survival (PFS) is defined by the time interval between the date of imatinib discontinuation and the date of first detection of GIST progression or death, whichever occurs first. Patients alive without progression are censored on the date of last follow-up Secondary:
	 Overall survival (the time period between the date of imatinib discontinuation and the date of death). Quality of Life (EQ-5D instrument).
	 Exploratory: To explore the relationship between study endpoints and blood biomarkers including, but not limited to, KIT/PDGFRA mutations in cell-free circulating DNA in plasma and circulating growth factor and cytokine levels. To explore the relationships between study endpoints and biomarkers in resected tumors prior to study entry. Changes in the blood cell counts and blood biochemistry after stopping imatinib as compared to the values on

	imatinib (includes comparisons in blood cell counts, serum transaminases, creatinine, and electrolytes between the baseline values measured on imatinib and the values measured at 2, 5 and 8 months after stopping imatinib).		
Pre-planned interim analysis:			
	• 1-year PFS in the first 15 patients included. The study is		
	terminated if 10 or more of the 15 patients (≥ 67 %) have		
	progression of disease or withdraws from the study within		
	the first 12 months from the date of study entry.		
STATISTICAL	This is a superiority study as compared with historical controls		
CONSIDERATIONS	regarding the main endpoint (PFS). Based on historical data,		
	discontinuation of imatinib in patients with metastatic GIST is		
	associated with rapid recurrence/progression. In the BRF-14		
	study where patients were randomised to discontinue imatinib at		
	1 and 3 years on treatment, the 2-years PFS was 10 % and 16 %,		
	respectively. Based on these observations, the historical 3-year		
	PFS can be assumed to be 15 %. An improvement in 3-year PFS		

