The primary objective of the study is to document progression-free survival (PFS) in patients who discontinue imatinib after treatment with imatinib for longer than 5 years for oligometastatic GIST (\leq 3 metastases) and who have no detectable overt GIST lesions in CT/MRI imaging following complete surgical resection (R0/R1-resection), radiofrequency ablation (RFA) of the metastases, or following systemic treatment for oligometastatic GIST

Secondary objectives

The secondary objectives are to study overall survival and the quality of life (QoL) in the patients who discontinue imatinib. Data about response to reinstitution of imatinib after GIST progression will be collected from the hospital records from those patients who restarted imatinib after completion of the study.

Exploratory objectives

The exploratory objectives are to study the relationship between study endpoints and circulating biomarkers, relationships between study endpoints and biomarkers in resected tumors prior to study entry, and changes in the blood cell counts and blood biochemistry after stopping imatinib as compared to the baseline values on imatinib, measured at the time of the screening examinations.

3 Investigational plan

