4.3 Study Monitoring

The investigator will be visited based on a monitoring plan (appendix I) by the Clinical Study Monitor, who will check the following:

- Informed consent process
- Adherence to protocol
- Maintenance of required regulatory documents
- The dates of study entry, GIST progression, TKI restarting and death
- Data completion on the CRFs including query resolution and source data verification (SDV).

The monitor will review the relevant CRFs for accuracy and completeness and will ask the site staff to adjust any discrepancies as required.

When the responsible study monitor has checked and verified the CRFs, the data will be entered into a computer database for further handling and statistical evaluation.

Sponsor's representatives (e.g. monitors, auditors) and/or competent authorities will be allowed access to source data for source data verification in which case a review of those parts of the hospital records relevant to the study may be required. Monitoring may be organized locally for each participating country.

5 Central pathology evaluation

The pathology reports from the primary tumour and metastasis will be sent to a Central Pathology Lab of the study located at the OUS, Norway, for evaluation. Tumour tissue samples of any deviant reports will be shipped for secondary review.

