11.1.3 Recording of data and retention of documents

The investigator must complete the CRF provided, must store copies of the CRF in a secure place and transmit the data to the OUS secretariat. Data on subjects collected on CRF during the trial will be documented in an anonymous fashion and the subject will only be identified by the subject identity number, and by his/her initials if also required. If, as an exception, it is necessary for safety or regulatory reasons to identify the subject, the investigators are bound to keep this information confidential.

The investigator must maintain source documents for each patient in the study, consisting of all demographic and medical information, including laboratory data, imaging results etc, and keep the signed informed consent form. All information on CRFs must be traceable to these source documents in the patient's file.

Essential documents, as listed below, must be retained by the investigator for as long as needed to comply with the national and international regulations. The investigator agrees to adhere to the document retention procedures by signing the protocol. Essential documents include:

1. IRB/IEC/REB approvals for the study protocol and all amendments,

- 2. all source documents and laboratory records,
- 3. CRF copies,
- 4. patients' informed consent forms (with study identity number and title of trial),
- 5. any other pertinent study document.

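### Follow-up laboratory results are to be recorded by circling a range, which does not fit the planned exploratory comparison of measured values before and after stopping imatinib

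*Protocol*

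**What the plan says.** **The recording rule.** Section 3.5.4.1 (Laboratory evaluations) states: "Laboratory values will be recorded on the Follow-up Form (circle the correct range) even when normal". No other section shown tells sites to enter the number, its unit or the local reference limits.

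**The planned use.** Among the exploratory assessments, the synopsis lists comparisons of blood cell counts and several chemistry items "between the baseline values measured on imatinib and the values measured at 2, 5 and 8 months after stopping imatinib". Section 2 repeats the aim as an exploratory objective: "changes in the blood cell counts and blood biochemistry after stopping imatinib as compared to the baseline values on imatinib".

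**Baseline.** The circling instruction names only the Follow-up Form. Section 3.5.2 says that recent haematology or biochemistry results "may be used as the Day 1 values", but not how they are entered.

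**Data flow.** Section 4.3 says that once the monitor has checked the CRFs, "the data will be entered into a computer database for further handling and statistical evaluation". Under section 11.1.3 sites must keep source documents, "consisting of all demographic and medical information, including laboratory data, imaging results etc", and the list of essential documents includes "all source documents and laboratory records".

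**The concern.** The objective is a change in a measured quantity within each patient. A circled range holds only the interval in which the result fell. If a result moves but stays inside the same interval, the form shows the same mark at both visits and the difference is stored as zero.

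The analysis runs on what the CRFs deliver. A site that follows section 3.5.4.1 to the letter would therefore supply data that support a table of category shifts and not the comparison of values that the synopsis describes. If baseline is entered as a number and follow-up as a range, the two halves of the pair are not even on the same scale.

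At stake is the precision of one exploratory endpoint. A later analysis plan cannot repair this alone, because it cannot analyse numbers that the form did not collect.

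**Working it through.** The protocol gives no sample size, power or test for the laboratory comparison, so there is no figure to reproduce. The check has two parts.

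**1. The sections side by side**

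- Synopsis and section 2 need, for each patient and test, a baseline value and values at months 2, 5 and 8.
- Section 3.5.4.1 provides, for the three follow-up visits, a circled range.
- Section 4.3 sends the CRF content to the database used for statistical evaluation.
- Section 11.1.3 keeps the laboratory records at the site.

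The numbers therefore exist, but under the natural reading the step that carries them to the database drops them.

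**2. Illustration of the information lost**

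Input from the protocol: n = 31 patients entered. Assumptions, none of them in the protocol: true shift d = 0.5 SD, correlation between baseline and follow-up ρ = 0.5 or 0.7, normal distributions, two-sided 5% test, no missing pairs.

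*With numbers (paired t-test).* The noncentrality is d·√n / √(2(1−ρ)).

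- ρ = 0.5: 0.5 × 5.568 / 1.000 = 2.78, power 0.77.
- ρ = 0.7: 0.5 × 5.568 / 0.775 = 3.59, power 0.94 (0.935 unrounded).

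*With two categories, in or out of range (exact McNemar test).* Only patients who change category carry information, and at least 6 such patients, all in one direction, are needed for p ≤ 0.05 (2 × 0.5⁶ = 0.031; 2 × 0.5⁵ = 0.063).

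| Out of range at baseline | Power, ρ = 0.5 | Power, ρ = 0.7 |
|---|---|---|
| 50% | 0.33 | 0.39 |
| 20% | 0.13 | 0.13 |
| 5% | 0.002 | 0.001 |

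The reason shows in the count of changers at ρ = 0.5. With 50% out of range at baseline, the chance of leaving the out-of-range category is 0.273 and of entering it 0.082. Together that is 0.355, or 31 × 0.355 = 11 patients expected to change. With 5% out of range the chances are 0.045 and 0.011, so 31 × 0.056 = 1.7 patients, usually too few for any significant result.

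*With more categories.* The loss shrinks quickly as bands narrow. Take haemoglobin with an assumed mean of 12.6 g/dL, SD 1.2, and change +0.5 with SD 0.9. Power with numbers is about 0.85. With cuts at 8, 10 and 12 g/dL it is about 0.1; moving the top cut to 13 gives about 0.3; bands of 1 g/dL give about 0.75.

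The direction of the loss is certain if only ranges are captured. Its size runs from slight to nearly total, depending on a form that is not in the document.

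**The case against.** The strongest reply is that the sentence says laboratory values will be recorded, and the Follow-up Form is not shown. A number might be written next to the circled range. The rule also names only the follow-up form, the measured results must be retained at the site, and the comparison is exploratory with no stated test or power target.

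All of this stands, and it limits the point. It does not remove it: circling is the only method the text gives, and sites work from the text. If the form does take a number, the sentence should say so.

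Three stronger readings are tempting but not supported:

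- *The comparison cannot be derived at all.* It cannot be derived from circled ranges in the database. Section 11.1.3 keeps the laboratory records, from which the numbers can be abstracted. The 20% source verification of tests and examinations in Appendix I does not bear on this: it checks what is on the form and neither adds numbers nor prevents later abstraction.
- *The trial would probably report no change because of the form.* That needs narrow assumptions about the cut-points and about effects staying within range. The adverse-event table in section 1.4 gives any-grade anaemia of 5% and 89%, leukopenia of 6% and 43%, and neutropenia of 8% and 41% on imatinib in two trials. Those are other populations, but they show that graded abnormalities, which ranges can register, may be common.
- *This is the only objective readout of benefit from stopping.* Weight, blood pressure and performance status are scheduled at every visit, section 3.5.6 follows the persistence or disappearance of imatinib adverse effects, and EQ-5D is a secondary endpoint.

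**Conclusion.** The concern holds in a limited form. The recording instruction in section 3.5.4.1 does not match the comparison of values in the synopsis and section 2. If followed as naturally read, it reduces that comparison, as far as the CRF data go, to shifts between categories.

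The conclusion rests on two readings: that circling a range means no number is entered, and that analysis uses the database built from the CRFs. The second is stated in section 4.3; the first is the natural sense of the text but cannot be confirmed without the form. The power figures are illustrations under assumed shifts, correlations and cut-points, and should not be quoted as properties of this trial.

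PFS, overall survival and quality of life are unaffected, and the source numbers are recoverable. Severity is minor, and the correction is a cheap improvement.

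**What to change.** In section 3.5.4.1, replace the parenthetical instruction to circle a range with one to record the numerical result, its unit and the local laboratory reference limits. State that this applies to the baseline form as well as to every follow-up form, so that both halves of each pair are on the same scale. Ranges or toxicity grades can then be derived centrally from the numbers if wanted.

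For patients already entered, transcribe the available results for baseline and months 2, 5 and 8 from the retained laboratory reports.

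The cost is a revised CRF page, a few more fields per visit and some back-entry, which grows the longer the change is delayed. It needs no additional sample or test.
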